### **13.3 PROCEDURES FOR HANDLING MISSING, UNUSED AND SPURIOUS DATA**

No imputation of values for missing data will be performed. Standard clinical monitoring and data management practices will be used to ensure the integrity of the data.

### **13.4 INTERIM AND ADDITIONAL ANALYSIS**

None.

## **14 MONITORING**

### **14.1 MONITORING OF CASE REPORT FORMS**

The study will be monitored by the Sponsor. Monitoring will be conducted per ICH GCP guidelines and Sponsor SOPs. The Monitor will visit the Investigator at regular intervals to review the progress and conduct of the study. The CRFs will be checked for completeness and accuracy against the patient records, charts, laboratory reports, and scans. Anonymity of the patient will be maintained at all times.

### **14.2 SAFETY DATA MONITORING**

The Medical Monitor will review and evaluate all toxicities causally associated with idronoxil (NOX66). Once the fourth patient of Cohort 1 has completed 1 Cycle or when appropriate, depending on the DLTs experienced, a determination will be made that enrolment to this cohort continue. Once the eighth patient in Cohort 1 has completed 1 treatment cycle or when appropriate, depending on the DLTs experienced, the next dose level may commence.

### **14.3 AUDITING**

Regulatory authorities, the HREC (Human Research Ethics Committee) equivalent or the Sponsor may request access to patient clinical notes and other relevant study documentation for an on-site audit or inspection at any time during or after study completion for quality assurance. The Investigator is obliged to facilitate this process by allowing full access.

## 15 ADVERSE EVENT REPORTING

Adverse events (AE) reported by the patient or observed by the Investigator will be listed individually on an adverse event form in the CRF. The signs and symptoms, time of onset, duration, treatment (if any), and follow-up procedures (if any) will be reported, and the criteria for assessing causality to study drug (Table 12) and outcome categories should be defined (Table 13).

### 15.1 DEFINITIONS

#### 15.1.1 AE

AE is any un-anticipated or unintended medical occurrence or worsening of a sign or symptom (including an abnormal laboratory finding) or disease in a study participant, which does not necessarily have a causal relationship with the study condition, procedures or study agent(s) that occurs after the informed consent is obtained.

#### 15.1.2 SAE

The definitions of SAEs are given below. The PI is responsible for ensuring that all staff involved in the trial are familiar with the content of this section.

An SAE or reaction is defined as any untoward medical occurrence that results in death, is immediately life-threatening, requires at least a 24-hour in-patient hospitalization or prolongation of existing hospitalization, results in persistent or significant disability/incapacity, or is a congenital anomaly/birth defect.

The definition of SAE also includes any important medical event. Medical and scientific judgment should be exercised in deciding whether expedited reporting is appropriate in other situations, such as important medical events that may not be immediately life-threatening or result in death or hospitalization, but may jeopardize the patient or may require intervention to prevent one of the other outcomes listed in the previous definition. These should also usually be considered serious. Examples of such events are intensive treatment in an emergency room or at home for allergic bronchospasm; blood dyscrasias or convulsions that do not result in hospitalization; or development of drug dependency or drug abuse. Progression of malignancy (including fatal outcomes), if documented by the use of an appropriate method (for example, as per RECIST criteria for solid tumours), should not be reported as an SAE and must be approved by the Sponsor.

Treatment within or admission to the following facilities does not meet the criteria of “in-patient hospitalization” (although if any other SAE criteria are met, the event must still be treated as an SAE and immediately reported):

- Emergency Department or Emergency Room

- Outpatient or same-day surgery units
- Observation or short-stay unit
- Rehabilitation facility
- Hospice or skilled nursing facility
- Nursing homes, custodial care or respite care facility

Hospitalization during the trial for a pre-planned surgical or medical procedure (one which was planned prior to entry in the trial), does not require reporting as a SAE to the Medical Monitor and Sponsor.

The definition of “related” is that there is a reasonable possibility that the drug caused any of the adverse events described in Table 12.

### 15.1.3 Guidelines for Determining Causality and Severity

The criteria used for determining the relationship between the study drug/s and the Adverse Event are shown below:

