#### **10.1.4 Definition and Determination of Dose Limiting Toxicity (DLT) and Maximum Tolerated Dose (MTD).**

The Maximum Tolerated Dose (MTD) of idronoxil as a monotherapy in the Phase Ia Run-In Arm will be defined as the dose level immediately below the dose level at which 2 of the first 4 patients per cohort (or at least 3 of 8 patients) during the first cycle of that particular Treatment Regimen experience DLT (related to therapy). Additional patients will be recruited so that at least 6 patients are treated at the designated MTD, with no more than 1 DLT observed among the 6 patients. The MTD will be defined in terms of NCI-CTC graded toxicity during the patients' treatment cycle (21 days).

A dose limiting toxicity (DLT) will be defined as any one of the following occurring during the first treatment cycle 1:

- NCI-CTCAE  $\geq$  Grade 3 neutropenia lasting  $\geq$  5 days OR febrile neutropenia (fever  $\geq$  38.5°C) Grade 4 thrombocytopenia, or Grade 3 thrombocytopenia associated with bleeding;
- NCI-CTCAE  $\geq$  Grade 3 abnormal laboratory values (except neutropenia and thrombocytopenia) that are assessed as clinically significant and causally associated with NOX66;
- NCI-CTCAE  $\geq$  Grade 3 non-laboratory toxicity that is assessed as causally associated with NOX66; (excluding alopecia, rash, nausea, diarrhea, and vomiting if controlled with standard supportive therapy);

Once any DLT is reported, at least two more patients will be enrolled at the same dose level. Escalation will continue only if a DLT is limited to one of 4 patients. If a DLT occurs in 2 or more patients, further dose escalation will cease and the MTD will be the next lower level.

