**Table 12. Adverse Event Relatedness Criteria to Study Drug**

Unlikely/unrelated:	An AE with a temporal relationship to drug administration, which makes a causal relationship improbable, and in which other drugs, chemicals or underlying disease provide plausible explanations.
Possible	An AE with a reasonable time sequence to administration of the drug, but which could also be explained by concurrent disease or other drugs or chemicals. Information on drug withdrawal may be lacking or unclear.
Likely	An AE with a reasonable time sequence to administration of the drug, unlikely to be attributed to concurrent disease or other drugs or chemicals, and which follows a clinically reasonable response on withdrawal (rechallenge) . Rechallenge information is not required to fulfil this definition
Certain	An AE occurring in a plausible time relationship to drug administration and cannot be explained by concurrent disease or other drugs or chemicals. The response to withdrawal of the drugs should be clinically plausible. The event must be definitive pharmacologically or phenomenologically using a satisfactory rechallenge procedure if necessary and feasible

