## 15.2 RESPONSIBILITIES FOR REPORTING

Investigators and the Sponsor are required by regulatory agencies worldwide to report adverse events which involve patients being administered a pharmaceutical product.

All serious adverse events (SAE) occurring from the signing of informed consent until 30 calendar days after last study treatment, whether related to drug or not, must be reported to the Medical Monitor and appropriate Sponsor contact person within 24 hours of first knowledge of the experience using the appropriate study SAE Report Form. SAEs are to be followed until resolution or stabilisation (with autopsy report if applicable).

Deaths and other SAEs occurring > 30 calendar days after last study treatment that are deemed 'possibly' or 'probably' related to the study treatment must be reported as SAEs on the SAE Report Form within 1 day of first knowledge of the event by the treating physician or research personnel (with an autopsy report if available).

Deaths occurring > 30 calendar days after study trial treatment and not attributed to study treatment (e.g., disease progression) need not be reported as SAEs, but simply captured on the appropriate CRF.

The investigative sites will send the SAE report to the Sponsor's Medical Monitor via fax or e-mail using the contact information below.

Primary Contact  Medical Monitor: [name] [name]	[contact] [contact] Email#: [contact]
Alternate Contact  Study Manager: [name]	[contact]; [contact] [contact] Email: [contact]

Pharmacovigilance (DATAPHARM Australia) Manager: [name]	[contact]; [contact] Email: [contact]
---	---

Transmission of the SAE Report Form should be confirmed by the site personnel submitting the report.

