8.2 Adverse events

Adverse events will be coded by MedDRA SOC and Preferred Term, summarised and tabulated for the safety population in the monotherapy arm (phase 1a), in combination arm (phase 1b) with low dose (AUC4) carboplatin and with high dose (AUC6) carboplatin and overall treatment. For each preferred term the number and percent of subjects reporting each adverse event will be tabulated by cohort and 'Overall'. These include:

- Adverse event summary table
- Adverse events occurring prior to study commencement
- All adverse events occurring after study commencement
- Most common (>15 %) treatment-emergent adverse events in any cohort
- Treatment emergent adverse events that were possibly, likely or certainly related to the study medication
- Serious adverse events
- Severe adverse events
- Adverse events causing withdrawal
- All adverse events by maximum severity and relationship to study treatment, with subject identification.

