11. TABLE AND FIGURE LISTINGS

Table Section	Table Title (Population)
Section 10.1	Patient disposition (All populations)
	Completion and withdrawal (Safety population)
Section 11.2	Demographics (Safety population)
	Disease history (Safety population)
	Prior medical history events (Safety population)
	Current medical history events (Safety population)
	Prior medications (Safety population)
	Concomitant medications (Safety population)
	New medications (Safety population)
	Prior chemotherapy (Safety population)
	ECOG status (Safety population)
Section 11.3	Compliance (Safety population)
Section 11.4	Tumour measurements (Efficacy population)
	RECIST response rates and durations (Efficacy population)
	Progression-free survival (Efficacy population)
	Overall survival (Efficacy population)
	Plasma concentrations (PK population)
	Pharmacokinetic coefficients (PK population)
Section 12.1	Exposure (Safety population)
Section 12.2	Summary of adverse events (Safety population)
	Pre-treatment adverse events (Safety population)
	Treatment emergent adverse events (Safety population)
	Treatment emergent adverse events considered possibly, probably or definitely related to study treatment (Safety population)
	Severe adverse events (Safety population)
	Adverse events resulting in withdrawal (Safety population)
Section 12.3	Deaths and serious adverse events
Section 12.4	Serum biochemistry (Safety population)
	Biochemistry shift table (Safety population)
	Haematology (Safety population)
	Haematology shift table (Safety population)
	Categorical urinalysis results (Safety population)

Section 12.5	Urinary pH and specific gravity (Safety population)
	Urinary microscopy (Safety population)
	Vital signs (Safety population)
	Physical examination (Safety population)
	ECG parameters (Safety population)
	ECG findings (Safety population)
	Biomarkers (Safety population)

Figure Section	Figure Title (Population)
Section 11.4	Tumour measurements (Efficacy population)
	Pattern of response by cohort (Efficacy population)
	Progression-free survival (Efficacy population)
	Overall survival (Efficacy population)
	Plasma concentrations by cohort (PK population)
Section 12.2	Most common preferred terms (Safety population)
Section 12.5	Biomarkers (for each parameter) (Safety population)

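### In the combination phases no separate causality rating is specified for NOX66 and carboplatin and 'study drug' is undefined, so related-event tables there cannot be reliably attributed to NOX66

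*Protocol*

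**What the plan says.** **How causality is rated.** Protocol 15.1.3 gives criteria for "determining the relationship between the study drug/s and the Adverse Event are shown below". Section 15 and the title of Table 12 use the singular, *study drug*. Within Table 12, an event is Possible if, despite reasonable timing, it "could also be explained by concurrent disease or other drugs or chemicals". Nothing says on which side of that contrast carboplatin falls, or how many ratings are recorded per event.

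**How the ratings are tabulated.** Protocol 13.2 plans tables by the highest relationship to study drug. SAP 8.2 lists "Treatment emergent adverse events that were possibly, likely or certainly related to the study medication". The table list in SAP 11 describes the same output as events "considered possibly, probably or definitely related to study treatment". None of these is split by agent. SAP 8.2 does report Phase Ia monotherapy, the AUC 4 combination and the AUC 6 combination separately, by cohort.

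**What the rules need.** One DLT criterion in Protocol 10.1.4 covers laboratory values "that are assessed as clinically significant and causally associated with NOX66", and the non-laboratory criterion also requires attribution to NOX66. Protocol 8.4 (intolerable event), 9.4 (continuing after an event of Grade 3 or worse in the Combination Arm) and 14.2 (Medical Monitor review) are all worded in terms of idronoxil.

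**Late reporting.** Protocol 15.2 sets a 1-day deadline for deaths and other SAEs more than 30 days after treatment "that are deemed 'possibly' or 'probably' related to the study treatment must be reported as SAEs".

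**The concern.** When two agents are given in the same cycle, a relatedness rating is interpretable only if the reader knows which agent it concerns. Here two investigators could rate the same Phase Ib event differently and both comply, because one counts carboplatin as a study drug and the other as an alternative explanation. SAP 3.3 gives four sites and plans no analysis by site, so such a difference would not be visible in the tables.

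At stake is what the combination phases can say about NOX66. The first primary objective (Protocol 6.1) covers tolerability both alone and with carboplatin. The design (Protocol 7) is non-randomised with no carboplatin-only arm, so investigator attribution is the main planned source on NOX66's share of combination toxicity. The rules that name NOX66 or idronoxil also act on a judgement that no specified data item clearly records, which makes them hard to audit.

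The category labels are a separate matter. A reporting deadline tied to words that are not on the rating scale may not reach the events it is meant for.

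**Working it through.** The documents give no figure on this point, so the check is mainly a comparison of texts, with simple arithmetic for size.

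**1. What is rated.**

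| Place | Object of the rating |
|---|---|
| Protocol 15, Table 12 title | study drug (singular) |
| Protocol 15.1.3 | study drug/s |
| Table 12, Possible and Likely rows | the drug, set against other drugs |
| Table 12, Certain row | plural, when it speaks of withdrawal |
| Protocol 13.2 | study drug; also study treatment |
| SAP 8.2 | study medication |
| SAP 11 | study treatment |

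None is defined for causality. Usage elsewhere does not settle it. Table 6, footnote 3, uses study drug for NOX66 and names carboplatin separately, whereas the heading of SAP 8.1 refers to study treatments in the plural.

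**2. One event under two readings.** Take a Grade 3 non-laboratory toxicity that begins after Day 2 and could be due to carboplatin.
- *Carboplatin is a study drug.* The carboplatin explanation counts towards relatedness. The event can reach Likely or Certain if Table 12's other conditions, including response to withdrawal, are met.
- *Carboplatin is an other drug.* The same explanation counts against relatedness. The event is Possible, or Unlikely/unrelated if the timing also makes NOX66 improbable.

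SAP 8.2 counts Possible as related. A shift from Likely to Possible therefore changes the relationship table but not the related-event count. Only a shift to Unlikely/unrelated changes the count.

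**3. Which rules are exposed.** Of the three DLT criteria in 10.1.4, the neutropenia/thrombocytopenia criterion carries no attribution to NOX66 and the other two do. Protocol 10.1.2 uses DLTs to set the combination MTD, and the only DLT definition is in 10.1.4. The rules in 8.4, 9.4 and 14.2 also apply while carboplatin is being given.

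**4. Size.**
- NOX66 dosing days in a full course: run-in 14; combination 6 × 7 = 42; total 56. Share in combination cycles: 42/56 = 75%.
- Cycles: 1 run-in + 6 combination = 7, so 6 of 7 involve both agents.
- One patient crossing between related and unrelated: 1/8 = 12.5 percentage points in a Phase I cohort; 1/12 = 8.3 to 1/10 = 10 points in a Phase IIa cohort of 10 to 12 (Protocol 10.1.3).
- Replacement patients may start at Phase Ib Cycle 1 (Protocol 8.5), and Phase IIa patients receive only the combination. Neither group supplies monotherapy data.

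**5. Category labels.**

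| Table 12 | SAP 8.2 | SAP 11 | Protocol 15.2, late events |
|---|---|---|---|
| Possible | possibly | possibly | possibly |
| Likely | likely | probably | probably |
| Certain | certainly | definitely | none |

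Even if probably is read as Likely, Certain has no counterpart in the 1-day rule. Protocol 15.2.2 sends late treatment-related SAEs to the Sponsor but gives no deadline.

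**The case against.** **The text does not say there is one pooled rating.** A reader might infer that each event receives a single rating against both agents together. The documents do not establish this: the eCRF is not among them, and the plural option in 15.1.3 could allow more than one rating. This stands, and the point is limited to what is specified. If the form does hold two ratings, the SAP still does not say which one to tabulate.

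**Study drug may simply mean NOX66.** Table 6 and the contrast in Table 12 support this. On that reading the recorded rating is the NOX66 rating, and the rules have their input. The reading is reasonable but not stated, and the plurals in 15.1.3 and in the Certain row pull against it. It would also leave no carboplatin rating, although Protocol 10.1.2 contemplates changes to either agent after a DLT.

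**NOX66 toxicity is visible elsewhere.** It would be too strong to say that the related-event tables cannot show it. Phase Ia is monotherapy and is tabulated separately, and no causality reading alters the all-causality tables. The objective can also be met at regimen level: NOX66 alone in Phase Ia, the combination in Phase Ib. All of this stands. The AUC 4 and AUC 6 columns, however, do not separate the agents, because both periods contain both.

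**Not every DLT depends on NOX66 attribution.** Correct: the cytopenia criterion does not, and the MTD sentence in 10.1.4 speaks of relation to therapy.

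**The late-SAE gap is narrow.** Probably is most naturally a synonym for Likely, so it is strained to count Likely as omitted, and 15.2.2 still requires a report. What remains is the missing counterpart for Certain in the 1-day rule.

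**Conclusion.** The concern holds for the combination phases. Without a rating specified for each agent, or a definition of study drug, related-event tables for Phases Ib and IIa cannot be reliably attributed to NOX66. The rules in Protocol 8.4, 9.4 and 14.2 and two of the three DLT criteria in 10.1.4 rest on an attribution that the specified data do not clearly capture. It does not hold for Phase Ia tables or the cytopenia DLT criterion.

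The 75% of dosing days assumes a full six combination cycles. The 12.5 points is per patient, not per event. It assumes a denominator of 8 and that the patient moves between related and Unlikely/unrelated with no other related event of the same preferred term. The documents give no basis for estimating how many patients would move.

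The label mismatch can be verified from the text alone: SAP 11 conflicts with SAP 8.2 and Table 12, and the 1-day rule in Protocol 15.2 does not name the strongest category.

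This should be corrected, but it does not undermine the all-causality safety tables. Ratings per agent would remain investigator judgements in an open-label study and would not replace a control arm.

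**What to change.** - **Protocol 15.1.3 and the AE form:** for each combination-phase event, record one Table 12 rating for NOX66 and one for carboplatin. State how the other agent is treated when each is rated.
- **SAP 8.2 and 11:** for Phases Ib and IIa, tabulate events related to NOX66, to carboplatin, and to either. Phase Ia tables stay as they are.
- **Protocol 15.2 and SAP 11:** replace the present labels with Possible, Likely or Certain, to match Table 12 and SAP 8.2.
- **Protocol 8.4, 9.4, 10.1.4 and 14.2:** the sponsor should reconcile these passages with the new ratings. Which attribution should govern DLT, withdrawal or continuation is a clinical decision and is not proposed here.

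The cost is one extra CRF field per event, a few extra table columns and some wording changes. It is best done while events are being collected, because attribution per agent is hard to reconstruct afterwards.

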**Table 12. Adverse Event Relatedness Criteria to Study Drug**

Unlikely/unrelated:	An AE with a temporal relationship to drug administration, which makes a causal relationship improbable, and in which other drugs, chemicals or underlying disease provide plausible explanations.
Possible	An AE with a reasonable time sequence to administration of the drug, but which could also be explained by concurrent disease or other drugs or chemicals. Information on drug withdrawal may be lacking or unclear.
Likely	An AE with a reasonable time sequence to administration of the drug, unlikely to be attributed to concurrent disease or other drugs or chemicals, and which follows a clinically reasonable response on withdrawal (rechallenge) . Rechallenge information is not required to fulfil this definition
Certain	An AE occurring in a plausible time relationship to drug administration and cannot be explained by concurrent disease or other drugs or chemicals. The response to withdrawal of the drugs should be clinically plausible. The event must be definitive pharmacologically or phenomenologically using a satisfactory rechallenge procedure if necessary and feasible

**Table 13: Adverse Event Outcome Category**

Resolved'	The patient has fully recovered from the adverse event with no residual effects observable.
'Resolved with Sequelae'	The patient has recovered from the adverse event, however there are residual effects observable.
'Ongoing'	The adverse event is still present and observable.
'Death'	The patient died as a result of the adverse event.
'Unknown'	The outcome of the adverse is unknown at the time of report.

